Study Protocol

Steroid Use for the Treatment of Non-RSV Bronchiolitis NCT04221087 11/9/2022

Study Protocol:

Scientific background: Bronchiolitis is the most common viral lower respiratory tract infection experienced by children < 24 months. The most common pathogen causing bronchiolitis is RSV, with the highest incidence of infection occurring throughout late winter/spring. Signs and symptoms include nasal congestion, cough, tachypnea, wheeze, and rales, and may progress to symptoms of respiratory distress (accessory muscle use, nasal flaring, head bobbing). While RSV is the predominant virus associated with bronchiolitis (up to 40% of cases), other viruses including rhinovirus, influenza, human metapneumovirus, and parainfluenza virus are also common causes. The second most common viral etiology of bronchiolitis is rhinovirus, which may account for up to 25%-40% of cases.

Bronchiolitis is one of the leading causes of hospitalization for young children. In 2002, it was estimated that bronchiolitis hospitalization costs totaled \$543 million, with a mean length of stay of 3.3 days. One study in 2013 indicated that although the incidence of hospitalizations for bronchiolitis decreased in the early 2000s, national healthcare utilization costs increased from \$1.34 billion to \$1.73 billion (a 30% increase). Due to the prevalence of bronchiolitis and high utilization cost, the American Academy of Pediatrics (AAP) issued an update in 2014 of the 2006 guidelines for the diagnosis, management, and prevention of bronchiolitis. These guidelines indicate that bronchiolitis should be diagnosed clinically and treated with supportive care, such as nasal suctioning, intravenous fluid administration, and supplemental oxygen if required. These guidelines specifically recommend against the use of bronchodilators, nebulized hypertonic saline, systemic corticosteroids, and antibacterials. Since these guidelines have been published, studies show that there has been on overall decrease in both healthcare utilization costs and length of admission, but that there has not been a significant impact on all-cause 7-day readmission rates.

While the treatment and management of RSV bronchiolitis has been extensively studied and validated, there is significantly less evidence to support similar management in children with non-RSV bronchiolitis. We conducted a literature review of over 120 articles related to the treatment of bronchiolitis with steroids. Many articles, including the AAP 2014 revised guidelines, discuss the limited use of steroids in the treatment of bronchiolitis. A 2007 PECARN multicenter study also showed no significant difference in hospitalization rate or re-admission rate with steroid use. These studies, however, do not differentiate between RSV and non-RSV bronchiolitis.

Studies evaluating the immune response to different viral etiologies of bronchiolitis indicate that there may be a significant difference in the pathophysiology of disease. For example, RSV bronchiolitis causes an increased expression of β glucocorticoid receptors (GR) with no increase in α -GR, leading to a lower ratio of α/β receptors, which has been associated with an insensitivity response to glucocorticosteroids. In contrast, human rhinovirus-associated bronchiolitis has been associated with a higher Th2 helper cell response leading to more histamine release than RSV, which causes a Th1 predominant response. Additionally, a meta-analysis from 2017 suggested that infection with rhinovirus leading to wheezing before the age of 36 months is associated with increased risk of developing asthma later in life, possibly through airway remodeling, epithelial release of cytokines, and upregulated expression of genes predisposing to asthma. The mechanism of action of corticosteroids revolves around the inhibition of initial inflammatory

responses such as vasodilation and chemotaxis of leukocytes to sites of inflammation. Since rhinovirus appears to have a different pathophysiology of immune response, it is possible that bronchiolitis secondary to other non-RSV viruses may respond to different immunomodulators, specifically steroids. This pilot study will contribute knowledge about the utility of steroid use in non-RSV bronchiolitis both clinically in terms of patient outcomes, and economically in terms of hospital utilization. If the proposed aims are achieved, this contribution will be significant because there may be reason to re-evaluate the current AAP Guidelines for diagnosis and management of bronchiolitis. We hypothesize that steroid use in this cohort will reduce length of stay, and subsequently reduce hospital costs through reduction of both 7-day same cause readmission rate and escalation of care (transfer to ICU).

In the short term, our work will address the feasibility of conducting a clinical trial assessing the utility and safety of steroid use in non-RSV bronchiolitis in the inpatient setting. Moreover, the work proposed here will develop a platform for a larger, multi-center double-blinded randomized control trial addressing the same question. This pilot study will establish expected target enrollment rates, adherence and drop-out rates, expected length of stay, and expected severity of disease assessed with the Kristjansson score at time of discharge for use in sample size and power calculations for future phase II/III trials. Thus, this work will be a foundational resource providing a research strategy and protocol for a larger scale trial.

Objectives: The long-term objective of this research is to improve the clinical course and outcomes of children diagnosed with non-RSV bronchiolitis. The objective of this proposal is to determine the efficacy of steroid use as a treatment modality in children < 24 months diagnosed with non-RSV bronchiolitis. The central hypothesis is that the use of standard airway- dose steroids (0.6mg/kg dexamethasone) will improve the clinical outcome of children hospitalized for non-RSV bronchiolitis, which will be evident by decreased length of stay. The central hypothesis was formulated based on data showing an interleukin response to rhinovirus that is dampened by steroid administration. The rationale underlying this proposal is that the completion of this research will identify a new treatment option for non-RSV bronchiolitis. The central hypothesis work may change the currently accepted practice guidelines for diagnosis and management of bronchiolitis. The central hypothesis will be tested by pursuing these specific aims:

1) To determine the extent to which steroid administration reduces hospital length of stay for clinical non-RSV bronchiolitis.

Hypothesis: Steroid administration will decrease duration of admission from time of admission from the emergency department (ED) to time of discharge instructions being printed.

2) To determine the extent to which steroid administration reduces the severity of bronchiolitis by using the Modified Tal Score to assess patients at admission, enrollment (if differs from admission time), 24 hours after administration of intervention, and discharge.

Hypothesis: Steroid administration will reduce the severity of bronchiolitis, which will be evident by a lower Modified Tal Score at 24 hours after medication administration.

Design/Methods: The study is a double-blind, randomized control trial. All participants will be treated with standard of care for viral bronchiolitis, including supportive care. All participants will also have had some form of viral testing confirming they do not have RSV or influenza. In

addition, half the participants will receive standard airway dosing of dexamethasone (0.6mg/kg) orally, and the other half will received placebo (sugar water 0.6mL/kg).

Eligibility Criteria:

Inclusion criteria:

- 1. Less than or equal to 24 months
- 2. First episode of wheezing or a clinical diagnosis of bronchiolitis
- 3. Admitted to the general pediatric service at UPMC Children's Hospital of Pittsburgh
- 4. Between 2/1/20 and 12/31/22
- 5. Ability of a parent or guardian to understand and comply with the study procedures
- 6. Signed written informed consent by parent or guardian
- 7. Respiratory viral testing obtained within 24 hours of admission

Exclusion Criteria

1. Preterm birth < 35 weeks

- 2. Presence of underlying cardiopulmonary, neuromuscular, or other complex disease
- 3. Admission to the PICU

4. Coinfection with influenza infection, RSV, acute COVID-19, or concomitant bacterial infection (such as pneumonia) as documented within the past 72 hours (per chart review)

5. History of allergy or reaction to steroids

6. History of an underlying chronic medical condition -including chronic heart disease, chronic lung disease (except asthma),congenital anomalies of the airways or lung, cystic fibrosis, chronic renal disease including nephrotic syndrome, protein losing enteropathy of any cause, severe malnutrition, glaucoma, neurocognitive disorders, metabolic disorders (including phenylketonuria, diabetes mellitus), or genetic disorders (note: genetic syndromes such as Down syndrome and Edwards Syndrome are excluded; however, children with genetic disorders (e.g., hemophilia) but who do not have a genetic syndrome may not satisfy this particular exclusion criterion; it is important that children with such genetic disorders do not have symptoms and/or comorbidities that would pose additional risk to them nor jeopardize the adequacy of study assessments.")

7. History of a condition that compromises the immune system -HIV infection, primary immunodeficiency, anatomic or functional asplenia; receipt of a hematopoietic stem cell or solid organ transplant at any time; receipt of immunosuppressive therapy including chemotherapeutic agents, biologic agents, antimetabolites or radiation therapy during the past 12 months; or daily use of systemic corticosteroids for more than 7 consecutive days during the past 14 days. 8. Any other condition that in the judgment of the investigator precludes participation because it could affect the safety of the subject

9. Any patient admitted to the inpatient general pediatrics teams from 4pm-9pm, as patients are to be enrolled in the study within 10 hours of admission and medication distribution cannot be complete until 7am.

10. Any patient who has previously received a dose of steroids medication in the emergency department within 24 hours prior to admission

Statistical Considerations: We will compare mean duration of hospital stay in the two treatment groups using the student T-test. As a secondary outcome we will compare mean scores on the Kristjansson scale (range 0 to 9) at each time point using generalized estimating equations

between the two treatment groups. Because this is a pilot study we will be underpowered, however, this study will provide data that will allow us to estimate the sample size needed for a future study. The number of time points to be used for the generalized estimating equation can be determined ad hoc to include a reasonably balanced sample to make the comparison valid.

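### Aim 2 times its key severity score from the dose but schedules no score at the dose, so the last pre-dose score can be about 0 to 10 hours old and no baseline is named

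*Combined protocol and SAP*

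**What the plan says.** Under Objectives, specific aim 2, the plan is to "assess patients at admission, enrollment (if differs from admission time), 24 hours after administration of intervention, and discharge". The accompanying hypothesis is a "lower Modified Tal Score at 24 hours after medication administration". Of these scores, only the 24-hour one is anchored to the dose.

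Exclusion criterion 9 covers "Any patient admitted to the inpatient general pediatrics teams from 4pm-9pm", for the reason that "patients are to be enrolled in the study within 10 hours of admission and medication distribution cannot be complete until 7am". The 10-hour limit is worded as running from admission to enrolment. No limit is stated for the interval from enrolment to dose.

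Statistical Considerations says that "we will compare mean scores on the Kristjansson scale (range 0 to 9) at each time point using generalized estimating equations". It adds that the number of time points in the model may be settled ad hoc, to obtain a reasonably balanced sample. It names no baseline score, no baseline covariate and no change from baseline.

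**The concern.** Aim 2 asks how far the steroid reduces severity. The natural reference for that is the child's state when treatment starts, and the schedule does not secure a score at that moment. The follow-up clock starts at the dose, while the pre-dose clock stops at admission or enrolment. The time between the two is not fixed and differs between children.

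Two things are at stake. First, any change from the pre-dose score, or any adjustment for it, would include a stretch of untreated course of varying length. Second, the separate enrolment time point exists only for children enrolled at a different time from admission. In a model that compares means at each time point, with the time points picked later for balance, that leaves the pre-treatment part of the model undefined.

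**Working it through.** The plan states no interval, sample size, standard deviation or correlation for the score, so there is no figure of its own to reproduce. The check is clock arithmetic on exclusion criterion 9.

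**Inputs**
- Admission to enrolment: at most 10 h (exclusion criterion 9).
- Study medication for late admissions: not complete before 07:00 (exclusion criterion 9).
- Excluded admission times: 16:00 to 21:00, so admissions from 21:00 onward are allowed (exclusion criterion 9).
- Key follow-up score: dose time + 24 h (specific aim 2).
- Assumption: children admitted overnight are dosed at 07:00.

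**Step 1: does the rule foresee a gap?** 07:00 − 10 h = 21:00, which is exactly the end of the excluded window. The criterion therefore appears to have been built around a wait of up to 10 h between admission and medication.

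**Step 2: age of the admission score at the dose** (07:00 − admission time), and its interval to the 24-hour score (age + 24 h).

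| Admission | Age at 07:00 dose | Interval to 24-hour score |
|---|---|---|
| 21:00 | 10 h | 34 h |
| 00:00 | 7 h | 31 h |
| 03:00 | 4 h | 28 h |
| 06:00 | 1 h | 25 h |

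**Step 3: age of the last pre-dose score.** Take a child admitted at 21:00.
- Enrolled on admission: there is one pre-dose score, 10 h old at the dose. The interval to the 24-hour score is 10 + 24 = 34 h.
- Enrolled at 07:00: the enrolment score is about 0 h old. The interval is 0 + 24 = 24 h.

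Two children admitted at the same hour and dosed at the same hour can thus have last pre-dose scores 10 h apart in age.

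**Step 4: effect on the planned analysis.** The stated comparison is of group means at each time point. At 24 hours it uses no earlier score, so the variable gap does not enter it. The gap enters only if a pre-dose score is used as a covariate, as the start of a change score, or as a time point in the GEE. How much precision would then be lost depends on the correlation of an older and a fresh score with the 24-hour score. The documents give neither, so no figure is offered.

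**The case against.** The strongest reply is that the plan never uses a baseline. It compares means, the 24-hour time point is anchored to the dose, and assignment is randomised and double-blind, so pre-dose gaps should balance between arms on average. That stands: this is not a bias, and the stated comparison remains valid.

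A second reply is that the words about enrolment differing from admission only avoid a duplicate. When the times coincide, the admission score is the enrolment score, so every child has a score at enrolment. That also stands. What varies is the distance of that score from the dose, and whether enrolment appears as a separate time point.

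A reader might infer more than the documents support:
- **A longer gap.** A child enrolled at 4pm and dosed at 7am would have a score 15 h old and an interval of 15 + 24 = 39 h. No explicit enrolment-to-dose limit forbids this. But nothing says that a child admitted before 4pm waits until 7am, and the match of 9pm + 10 h with 7am suggests that the 10 h was meant to reach the dose.
- **An admission score taken before consent, or drawn from the chart.** Inclusion criterion 6 requires "Signed written informed consent by parent or guardian" but gives no timing, and enrolment at admission is allowed. No source for the scores is stated.
- **Weaker planning figures.** The severity figure that the background section wants for future trials is the score at discharge, which pre-dose timing does not affect.
- **A quantified loss of variance reduction.** Any such number would rest wholly on assumed correlations and on an adjustment that is not planned.

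**Conclusion.** The point holds as a gap in the assessment schedule. No score is tied to the dose, none is named as the baseline, and the time from enrolment to dose has no stated limit. If overnight admissions are dosed at 7am, the last pre-dose score is about 0 to 10 h old and the interval from it to the 24-hour score is about 24 to 34 h. If the 10-hour limit is read as covering enrolment only, the documents set no upper bound.

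The consequence is limited. The comparison of arms at 24 hours is sound in this respect. A change-from-baseline or baseline-adjusted estimate would be blurred by an amount that cannot be computed here, and the pre-treatment time point in the GEE is left open. For a secondary outcome in a pilot that describes itself as underpowered, this is a worthwhile and inexpensive improvement. It is worth making also because the protocol is meant to serve as the basis for a larger trial.

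**What to change.** In specific aim 2, replace the conditional enrolment score with a bedside score in every child immediately before the study dose, on the same scale as the follow-up scores. (Aim 2 and Statistical Considerations name different scales, so the one in use must be settled.) Name this score as the baseline. In Statistical Considerations, name it as the pre-treatment time point for the GEE, for example as a covariate in the 24-hour comparison. Record the clock times of the score and of the dose. Keep the admission score as a descriptive item.

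This gives every child the same interval of about 24 h between the pre-dose and key follow-up scores, and a pre-treatment time point planned for all children. It moves an assessment already planned, adds no visit and leaves treatment unchanged. The cost is a wording change in two sections and one score that must coincide with dosing, including early-morning doses.

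### Exclusion 10 covers only steroid given in the emergency department before admission, so a child given systemic steroid elsewhere, or on the ward before the blinded dose, stays eligible

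*Combined protocol and SAP*

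**What the plan says.** All of the relevant text but one item is in Eligibility Criteria.

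- **Exclusion 10** removes "Any patient who has previously received a dose of steroids medication in the emergency department within 24 hours prior to admission".
- **Exclusion 7** is the only other steroid rule. It applies in any setting, but only to "daily use of systemic corticosteroids for more than 7 consecutive days during the past 14 days".
- **Exclusion 8** is discretionary and tied to safety: "Any other condition that in the judgment of the investigator precludes participation because it could affect the safety of the subject".
- **Exclusion 9** removes "Any patient admitted to the inpatient general pediatrics teams from 4pm-9pm", on the ground that "patients are to be enrolled in the study within 10 hours of admission and medication distribution cannot be complete until 7am".
- **Objectives, aim 2** schedules a severity score at "enrollment (if differs from admission time", so enrolment is expected to follow admission for some children.
- **Exclusion 6** lists "chronic lung disease (except asthma" with asthma spared, and **inclusion 2** reads "First episode of wheezing or a clinical diagnosis of bronchiolitis".

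On background care, Design/Methods gives every participant usual supportive treatment for viral bronchiolitis. The Scientific background reports that the paediatric guideline advises against systemic corticosteroids. Nothing in the document expressly bars open-label steroid.

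**The concern.** The evident purpose of exclusion 10 is to compare dexamethasone with placebo in children who have no recent steroid on board. The event that matters for that purpose is the blinded dose. The rule is tied instead to admission and to one location, which leaves two openings:

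- **Another setting before admission.** A dose given in a clinic, for example, in the preceding 24 hours.
- **The ward after admission.** A dose given between admission and the blinded dose.

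A pre-treated child on placebo is a steroid-treated control. A pre-treated child on active drug receives a second steroid exposure that a tighter rule would have avoided. Both pull the observed difference in length of stay and in the 24-hour severity score below what it would be in steroid-free children. That has some relevance because the pilot's data are meant to feed the sample size of a later trial.

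**Working it through.** The document gives no sample size, SD, target effect or rate of prior steroid use, so there is no stated figure to reproduce. The check is a reading of the criteria, a clock calculation, and an illustration with labelled assumptions.

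**1. Does another criterion close the openings?** Take one systemic dose in a clinic six hours before admission, or one dose on the ward three hours after it. Exclusion 10 catches neither, because the first has the wrong setting and the second has the wrong setting and time. Exclusion 7 catches neither, because it needs more than 7 consecutive days. Exclusion 8 may catch either, but only if the investigator judges a safety risk. The sentence on background care describes treatment and is not an eligibility rule.

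**2. How long is the uncovered ward interval?** Exclusion 9 limits enrolment to 10 hours from admission and sets no time to dose. If the 7am remark means that study drug is not released before 7am:

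- Admission at 9pm: 3 + 7 = 10 hours to 7am, which matches the enrolment limit.
- Admission at 4pm: 8 + 7 = 15 hours, over the limit, which would explain the excluded block.
- Eligible clock hours: 24 − 5 = 19. Hours with a built-in wait (9pm to 7am): 10, and 10/19 = 53% of eligible clock hours.
- Average wait for those admissions, if spread evenly (assumption): 10/2 = 5 hours.
- For a 9pm admission, the last 10 of the 24 + 10 = 34 hours before the dose have no short-term steroid rule: 10/34 = 29%.

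**3. How much dilution?** Let *q* be the fraction pre-treated in both arms and *m* the share of its usual benefit that the blinded dose still gives them. The fraction of the difference that remains is 1 − *q*(1 − *m*). For a scale in hours, the mean stay in the Scientific background is 3.3 days × 24 = 79.2 hours. An assumed true reduction of 10% or 20% is then 7.92 or 15.84 hours.

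| Assumed *q* | Remaining, *m* = 0 | Remaining, *m* = 0.5 | Hours lost, 10% effect, *m* = 0 | Hours lost, 20% effect, *m* = 0 |
|---|---|---|---|---|
| 2% | 0.98 | 0.99 | 0.16 | 0.32 |
| 5% | 0.95 | 0.975 | 0.40 | 0.79 |
| 10% (unlikely) | 0.90 | 0.95 | 0.79 | 1.58 |

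**4. Against sampling error.** Assume a 0.5 SD effect and 20 or 50 children per arm. The standard error is √(2/20) = 0.316 SD or √(2/50) = 0.200 SD. At *q* = 2% and *m* = 0 the loss is 0.5 × 0.02 = 0.01 SD, or 0.03 to 0.05 of a standard error. At *q* = 10% it is 0.05 SD, or 0.16 to 0.25 of a standard error.

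**5. For the later trial.** If the diluted difference were used as the planning value, required N would rise by 1/(1 − *q*)² at *m* = 0: 1.04 at 2%, 1.11 at 5%, 1.23 at 10%.

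**The case against.** The strongest reply is that this is a drafting preference with no visible consequence. The main route, the emergency department, is already closed. The guideline advises against steroids and all participants receive usual care, so open-label steroid on the ward would depart from the described management. Aim 1 starts the stay clock at admission from the emergency department, so that is the expected path in, and it narrows the clinic route. The children are at most 24 months old, and exclusion 2, on underlying cardiopulmonary disease, may be read to remove asthma despite the exception in exclusion 6. Statistical Considerations already concedes that the pilot is underpowered. Every dilution figure rests on assumed rates.

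Most of this stands, and it is why the point is minor. It narrows the openings without closing them. Arriving through the emergency department does not bring a dose given earlier, elsewhere, under exclusion 10, and inclusion 3 does not require that path. The description of usual care makes no exposed child ineligible. The alternative wording in inclusion 2 also admits a child with earlier wheeze, though no text says that such children receive steroid before the blinded dose.

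Three stronger readings are tempting and are not supported:

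- **That children wait up to 10 hours for the dose.** The 10-hour limit is on enrolment. The wait is inferred from the 7am remark and reaches 10 hours only for a 9pm admission.
- **That 53% or 29% measures risk.** These are shares of clock time, not of patients or of exposures.
- **That the comparison is biased.** Steroid given before the blinded dose cannot depend on the effect of that dose, and with allocation blinded it is balanced between arms on average.

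**Conclusion.** The gap in wording is real. A single systemic dose outside the emergency department in the 24 hours before admission, or on the ward before the blinded dose, does not make a child ineligible except at the investigator's discretion on safety grounds.

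The consequence is a small dilution, with the randomised comparison still valid, and an avoidable second steroid exposure in the active arm. The documents show no harm from that second exposure. At an assumed 2% pre-treated, with no added benefit from the blinded dose, about 2% of the difference is lost. That is 0.2 to 0.3 hours of stay if the true reduction is 10% to 20% of 3.3 days. The document gives no pre-treatment rate. Rates as high as 10% fit poorly with the closed emergency department route and the guideline's advice.

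Severity: minor. This is a cheap improvement, justified by the low cost of the change and not by the size of the loss.

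**What to change.** Reword exclusion 10 to: *any systemic corticosteroid, in any setting, from 24 hours before admission until the blinded dose*. Check the medication record and ask the parent just before study drug is released. Keep any child found after randomisation to have been pre-treated in the randomised arm for analysis.

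Two additions are optional: a look-back longer than 24 hours for short outpatient courses, which is the sponsor's choice, and a report by arm of open-label systemic steroid given after the blinded dose.

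The cost is one reworded criterion, one medication check and a few fewer eligible children. There are no extra visits and no change to care.

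### Length of stay is compared by an unadjusted t-test although a pre-dose severity score is already scheduled and low power is conceded; pre-specify that score as a covariate once the plan settles which scale it is

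*Combined protocol and SAP*

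**What the plan says.** The Statistical Considerations section gives the whole length-of-stay analysis in one sentence: "We will compare mean duration of hospital stay in the two treatment groups using the student T-test". No covariate or adjusted model is named there or elsewhere. Length of stay is the subject of aim 1 under Objectives, where the clock is "duration of admission from time of admission from the emergency department (ED) to time of discharge instructions being printed". No outcome is labelled primary. Length of stay is primary by inference, because the score comparison is called secondary.

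Aim 2 schedules severity assessment "using the Modified Tal Score to assess patients at admission, enrollment (if differs from admission time), 24 hours after administration of intervention, and discharge". The first two of these come before the intervention.

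Two scales are named. Aim 2 uses the Modified Tal Score. The background says the pilot will establish "expected severity of disease assessed with the Kristjansson score at time of discharge for use in sample size and power calculations", and the statistical section says "As a secondary outcome we will compare mean scores on the Kristjansson scale (range 0 to 9) at each time point".

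On power, the plan says only "Because this is a pilot study we will be underpowered". It gives no sample size, alpha, target difference or SD.

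**The concern.** A pre-dose measure of how ill the child is may predict how long the child stays. Where it does, a model containing it removes part of the between-child variation from the treatment comparison. It also removes the linear effect of any chance difference in entry severity between arms. The t-test does neither.

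This matters here for two reasons. Aim 1 asks how much stay is reduced, so interval width is what the trial delivers on its main question, and the plan expects low power. The pilot is also meant to supply inputs for a future sample size. If that trial adjusts for severity, its planners need the residual SD, which a t-test does not give.

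The covariate cannot be written into the plan as it stands, because the plan does not settle which scale is scored.

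**Working it through.** The plan has no figure to reproduce, so the check is how much adjustment could change.

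**Inputs.** From the documents: 1:1 allocation, and a mean stay of 3.3 days (Scientific background; 3.3 × 24 = 79.2 h), which is a 2002 figure for bronchiolitis admissions generally. Assumed: two-sided 5% level; 20 to 40 per arm; coefficient of variation 0.6 (SD 0.6 × 79.2 = 47.5 h); 25% reduction in mean stay; within-arm correlation r between pre-dose score and stay from 0 to 0.5.

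**Large-sample gain.** Adjustment multiplies the variance of the treatment difference by 1 − r², so effective sample size rises by 1/(1 − r²) − 1:
- r = 0.1: 1/0.99 − 1 = 1%
- r = 0.2: 1/0.96 − 1 = 4%
- r = 0.3: 1/0.91 − 1 = 10%
- r = 0.5: 1/0.75 − 1 = 33%

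**Small-sample cost.** Estimating the slope costs one degree of freedom and inflates the variance by about 1 + 1/(2n − 4), with n per arm. The CI width ratio, adjusted to unadjusted, is √[(1 − r²)(1 + 1/(2n − 4))] times the ratio of t quantiles on 2n − 3 and 2n − 2 degrees of freedom. At n = 40 the inflation is 1 + 1/76.

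**Power.** 20,000 simulated trials per setting, lognormal stays, analysed on the raw mean scale:

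| r | CI width ratio, 40/arm | Power 40/arm, t-test → adjusted | Power 20/arm, t-test → adjusted |
|---|---|---|---|
| 0 | 1.007 | 0.576 → 0.571 | 0.322 → 0.311 |
| 0.1 | 1.002 | 0.574 → 0.572 | 0.320 → 0.317 |
| 0.2 | 0.986 | 0.572 → 0.583 | 0.326 → 0.326 |
| 0.3 | 0.960 | 0.575 → 0.609 | 0.316 → 0.336 |
| 0.5 | 0.872 | 0.570 → 0.692 | 0.319 → 0.397 |

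With normal stays at 40 per arm the width ratios are the same. Power is 0.455 → 0.449 (r = 0), 0.460 → 0.490 (r = 0.3) and 0.455 → 0.563 (r = 0.5), so the gain does not depend on skew. With no treatment effect, both methods reject in 4.6% to 5.2% of trials.

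**Break-even.** The width ratio equals 1 at r of about 0.12 with 40 per arm and 0.17 with 20.

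**Chance imbalance.** The probability that mean entry scores differ by 0.3 SD or more is 2[1 − Φ(0.3√(n/2))]: 34%, 25% and 18% at 20, 30 and 40 per arm. Such a difference moves the unadjusted estimate by 0.3 × r × 47.5 h: 1.4 h at r = 0.1 and 7.1 h at r = 0.5.

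**Next trial.** For an assumed difference of 0.5 SD and 80% power, the normal approximation gives 63 per arm unadjusted, and 61, 58 and 48 adjusted at r = 0.2, 0.3 and 0.5.

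**The case against.** The strongest reply is that nothing is wrong: a t-test is a legitimate analysis of a randomised two-arm trial, and preferring adjustment is a matter of efficiency. That stands, and it sets the weight of the point.

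The benefit also rests on an r that the documents do not give. Eligibility may hold r down: PICU admissions and children with complex or chronic disease are excluded, which narrows the severity range. At 20 per arm and r = 0.2 the power gain is nil. This also stands. The 1% large-sample gain at r = 0.1 should not be read as a real gain, since the interval at 40 per arm is 0.2% wider there.

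The imbalance figures are not a second loss. Chance imbalance is already in the unadjusted standard error, which is 47.5 × √(2/40) = 10.6 h at 40 per arm, so shifts of 1.4 to 7.1 h are 0.13 to 0.67 standard errors. That is correct: they show the same loss as it appears in a single trial.

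The t-test needs no score, whereas the model would drop children without one. At r = 0.3 and 40 per arm, 0.960² = 0.922, so about 8% missing scores would cancel the gain. Nothing in the documents says pre-dose scores will be missing, as the clause leaving the number of time points open names no visit. A routine rule for a missing baseline value meets the objection.

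Finally, a pilot exists to feed the next design, and the t-test analysis already supports the unadjusted SD. It does not supply the residual SD. The scale conflict is a defect in its own right because it affects the secondary outcome directly. Here it matters only because it blocks naming the covariate.

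**Conclusion.** The concern holds as a change to consider. The plan leaves an already scheduled pre-dose score out of its length-of-stay comparison. Any loss is in precision alone; validity and the error rate are unaffected. Under the assumptions above, the gain is absent below r of about 0.12 to 0.17, modest at 0.3 (interval 4.0% narrower, power up 3.4 points at 40 per arm) and material at 0.5 (12.8% narrower, up 12.2 points at 40 per arm, 7.8 at 20). Adjustment would not make the pilot adequately powered. The value of reporting a residual SD for the next trial does not depend on r.

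**What to change.** 1. State whether the severity score is the Modified Tal or the Kristjansson, and use that name throughout.
2. Replace the t-test with a linear model of length of stay, on the clock defined in aim 1, with treatment arm and one pre-specified covariate: the enrollment score, or the admission score where the two coincide, recorded before the first dose.
3. Report the adjusted mean difference with its 95% CI, with the unadjusted difference alongside.
4. Report the unadjusted SD, the residual SD and the score-to-stay correlation for planning the next trial.
5. State a rule for a missing pre-dose score, such as simple baseline imputation made without regard to arm, so that no child is dropped.
6. A log-scale analysis may be added as a sensitivity analysis only.

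Fix this before unblinding, so that the covariate is not chosen after results are seen. The cost is SAP wording and reconciling the scale name; the score is already scheduled, so no new data are needed. If the score proves uninformative, the simulated loss of power is 0.5 point at 40 per arm (0.576 − 0.571) and 1.1 points at 20 (0.322 − 0.311).
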